12. DATA REPORTING REQUIREMENTS

Adverse event lists, guidelines, and instructions for AE reporting can be found in Section 7.0 (Adverse Events: List and Reporting Requirements).

12.1 Data Reporting

12.1.1 Method

This study will be monitored by Ohio State University (Coordinating site) per their institutional guidelines for Multicenter Trials. Cumulative protocol- and patient-specific data will be submitted via Case Report Forms to The Ohio State University within 2 weeks of patient completion of each cycle/study time point.

12.1.2 Case Report Forms:

Case Report forms will be provided by OSU. In addition to case report forms, relevant reports on source documents will be requested to verify objective response. Actual CT or MRI images might be requested to verify objective response.

13. STATISTICAL CONSIDERATIONS

13.1 Study Design/Endpoints

13.1.1 Study Overview

This is a randomized phase II study designed to screen two different regimens and identify which one is the more promising candidate for subsequent testing in a Phase III trial in metastatic, radioiodine-refractory differentiated thyroid cancer (DTC) patients with mutated BRAF. To determine this, this study will assess the proportion of patients who have any response (minor, partial, or complete) within 6 cycles of therapy. Patients will be randomized to receive one of the two treatment regimens with equal allocation. Randomization will be done using block randomization with varying block sizes.

13.1.2 Primary Endpoint

The primary endpoint for each of the treatment arms of this trial is overall objective response rate, defined as the proportion of patients who have a minor response (MR), partial response (PR), or complete response (CR) within the first 6 cycles of therapy. All randomized patients meeting the eligibility criteria who have signed a consent form and have begun treatment will be evaluable for response.

Complete response (CR) and partial response (PR) will be defined by RECIST 1.1, and minor response (MR) will be defined as 20-29% decrease in the sum of diameters of target lesions, taking as reference the baseline sum diameters. Any patients who have received at least one dose of treatment will be considered evaluable for these analyses. Patients will be analyzed in the treatment arm to which they were randomized. If a patient progresses, they will have met the primary endpoint classification for the purposes of this protocol (i.e. they will have had a response prior to progression or not). Patients' statuses prior to progression will be used in the assessment of response rates when evaluating the

primary endpoints for the treatment arms. Data on patients who cross over and receive treatment per another arm after progression will not be used in the decision analyses.

Rationale for using minor response as a part of objective response: Currently, many targeted therapy trials show clinically meaningful responses that are most evident only when reviewing waterfall plots that show % of tumor shrinkage in each patient. We have learned that PR and CR do not provide accurate assessment of clinical benefit. While stable disease is included as part of objective response in many solid tumors, it is not interpretable in patients with thyroid cancer due to overall slow-growing nature of cancer in many patients. Per RECIST 1.1, > 20% increase in tumor target lesions is considered significant and objective response in this case is defined as progressive disease. We therefore believe that 20-29% shrinkage of tumor represents true shrinkage that is clinically meaningful and is not by chance or measurement variation. Thus, we include MR as a part of objective response even though MR is not conventionally included.

13.1.3 Statistical Design

To both evaluate whether or not each of these experimental treatment regimens are sufficiently active in this patient population as well as to screen these regimens for the most promising regimen to be carried forward to the phase III setting, this study utilizes a flexible screening design developed by Sargent and Goldberg (*Statistics in Medicine*, 2001). Overall, we have developed this study to be able to determine that one regimen is decidedly worth pursuing further over another if the true differential in the overall response rates between arms is 0.20. Overall, we have developed this study to be able to determine that one regimen is decidedly worth pursuing further over another if the true overall response rates are 15% versus 35%. This study design has 90% power to identify the correct regimen as most promising and thus the regimen to bring forward into larger and confirmatory studies. Based on these assumptions and constraints, 26 evaluable patients will be accrued to each arm to evaluate the regimens under the parameters specified. If our underlying assumptions regarding the true response rates associate with each of these arms is a little lower (e.g. 10% vs. 30%), we will have additional power for these analyses (i.e. >90%). Even if our true response rates corresponding to the treatment regimens being evaluated here are higher (e.g. 40% vs. 60%), we will still have sufficient power (>88%) to determine that one arm is more promising than another if it truly is with this number of patients per arm and the same rule for observed differential described below. The main decision rule is based on differential, and the above assumptions show a flexibility and sufficient power for identifying the most promising regimen even if our hypotheses regarding response rates are slightly off.

As part of this design, we define one treatment arm to be more promising than another if the actual observed overall response rate for each of the arms differ by 10% or more, in which case the regimen with the higher overall response rate will be recommended for further testing. If these rates differ by less than 10%, factors

other than the overall response rate will be considered.

- If one treatment arm has an overall response rate that is at least 0.10 higher than the other, then it will be deemed the most promising and carried forward to the phase III setting.
- If the rates of the arms fall within $d = +/- 0.10$ of each other, the results of the study are considered statistically ambiguous and the regimens are considered similar with respect to their respective overall response rates. In this case, other factors are allowed to be taken into consideration when deciding on which regimen to bring forward into definitive Phase III testing. For this trial, we will specifically evaluate differences in the toxicity, PR+CR rate, progression-free survival, and correlative markers that indicate if the inhibitor therapeutic agents are hitting their respective targets.
- In the event that the success rates fall within .10 of each other, this study design assumes that there is a 50/50 chance of choosing the correct regimen. However, the choice of “d” used to determine whether or not other factors are considered is decidedly wide in order to allow the incorporation of the toxicity, translational, and other efficacy endpoints to be taken into consideration in this complex patient population. If one is clearly more promising than the other regimens and thus surpasses the other by the stated “d”, then it is less relevant to utilize other factors in this determination. The only potential exception is if the clearly most promising regimen has substantially more toxicity than the other regimen(s).

13.2 Sample Size/Accrual Rate

13.2.1 Sample Size

The one-stage screening design to be utilized as described in Section 13.1. A maximum of 26 evaluable patients will be accrued to each arm unless undue toxicity is encountered. Overall, a total of 52 patients will be accrued to this trial (26 to each of the two treatment arms).

13.2.1 Accrual Time and Study Duration

Based on previous studies conducted through this group in this patient population, we expect the annual accrual rate to be approximately 7 patients per quarter. Therefore, the accrual period for this trial is expected to be about 24 months. The total study duration is expected to be 4 years, in order to fully evaluate clinical outcomes.

The primary endpoint analysis will be done after the last accrued patient

has been followed for at 6 cycles. The primary endpoint analysis will be done after the last accrued patient has been followed for at 6 cycles.

13.3 Stratification Factors

None

13.4 Analysis of Secondary Endpoints

The MR+PR+CR response rate will be estimated for each treatment arm. In determining this rate, the number of patients with RECIST-based MR, PR or CR will be divided by the number of evaluable patients. All evaluable patients will be used for this analysis. Exact binomial 95% confidence intervals for the true PR+CR response rate will be calculated.

The Kaplan-Meier method will be used to estimate progression-free and overall survival. Each of these variables will be measured from the date of registration to the date of the event (i.e., death or disease progression) or the date of last follow-up to evaluate that event. We will also evaluate the proportion of patients who are progression-free and alive at one year.

Toxicity and Tolerability: Frequency and severity of adverse events and tolerability of the regimen in each of the treatment arms will be collected and summarized using descriptive statistics. As per NCI CTCAE v4.0, the term toxicity is defined as adverse events that are classified as either possibly, probably, or definitely related to study treatment. The maximum grade for each type of toxicity will be recorded for each patient, and frequency tables will be reviewed to determine toxicity patterns. In addition, we will review all adverse event data that is graded as 3, 4, or 5 and classified as either “unrelated” or “unlikely to be related” to study treatment in the event of an actual relationship developing. The incidence of severe (grade 3+) adverse events or toxicities will be described. We will also assess tolerability of the regimens through assessing the number of patients who required dose modifications and/or dose delays. In addition, we will also capture the proportion of patients who go off treatment due to adverse reactions or even those who refuse further treatment for lesser toxicities that inhibit their willingness to continue participation on the trial. These tolerability measures will be assessed within each of the treatment arms and we will explore differences in these measures between the arms. All patients who have received at least one dose of any of the therapeutic agents in a treatment arm will be evaluable for toxicity and tolerability.

In addition to the clinical outcomes of interest, we will also evaluate several correlative markers as well. Specifically, we will evaluate the serum thyroglobulin and assess how these levels correspond with achievement of response to treatment. We will assess this as between and across treatment arms; change in serum thyroglobulin levels will be evaluated between arms, and the impact of this change and how it is associated with response will be assessed using logistic regression analyses; we will look at how treatment arm and thyroglobulin levels are associated

with incidence of response. We will also evaluate differential levels using graphical methods (e.g. side-by-side boxplots) and two-sample t-tests (or nonparametric equivalent as necessary). We will also evaluate pharmacokinetic, pharmacogenetic, and pharmacodynamic markers. Differences in these markers and factors between patients who do vs. do not achieve response will be evaluated using chi-square statistics and two-sample t-tests depending on the type of marker/factor being compared based on clinical outcome group. Graphical analyses will also be used to assess potential trends and relationships between clinical response and these markers/factors.

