[name]
Columbus, OH 43202
Email: [contact]

Novartis Supplied Agents: Tafinlar (Dabrafenib) and Mekinist (Trametinib)

Protocol Type /Version Date: October 03, 2017

SCHEMA

A Randomized Phase 2 Study of single agent Dabrafenib (BRAFi) vs. combination regimen Dabrafenib (BRAFi) and Trametinib (MEKi) in patients with BRAF mutation or BRAF gene fusion defect in thyroid carcinoma

Locally Advanced or Metastatic Iodine Refractory Differentiated Thyroid Cancer Harboring BRAF mutation or BRAF gene fusion

- Measurable ds
- Progressive ds per RECIST v1.1 in 13-months prior to study entry
- No more than 3 prior multikinase inhibitors therapy

1⁰ Endpoint: Objective Response
Single Stage Design
Total Sample size=52
1:1 Randomization

ARM A: Dabrafenib (BRAFi) 150 mg orally twice daily

N=26 patients

If progression on
ARM A, may
cross-over to
ARM B

ARM B: Dabrafenib (BRAFi) 150 mg orally twice daily and Trametinib (MEKi) 2 mg orally once daily

N=26 patients

Continuous treatment until disease progression, unacceptable adverse event, consent withdrawal, or development of illness prohibiting further treatment.

Adverse Event assessment every 2 weeks for the first 8 weeks, and then every 4-8 weeks thereafter (4 weeks = 1 cycle)

Tumor Markers & Response Assessment by CT scan or MRI scan every 8 weeks
PET scans pre –study and at 8 weeks as clinically indicated

Correlative Studies:

1. Signaling inhibition studies in tumor biopsies (7 pts in each arm; 3-5 pts per center)
2. BRAF mutation studies in circulating plasma DNA (all study patients)
3. Mechanisms of drug resistance in tumor biopsies or tumor blocks (5 pts in each arm)
4. Assess predictors of response (Archival tumor block/unstained slides in all study patients)
5. Pharmacokinetic studies (First 7 pts enrolled on each arm)
6. Pharmacogenomics studies (All study patients)

TABLE OF CONTENTS

| | Page |
|---|------|
| SCHEMA | v |
| 1. OBJECTIVES | 9 |
| 1.1 Primary Objectives | 9 |
| 1.2 Secondary Objectives | 9 |
| 2. BACKGROUND | 9 |
| 2.1 Thyroid Cancer | 9 |
| 2.2 The Role of BRAF mutation in Thyroid Cancer | 10 |
| 2.3 Dabrafenib (BRAFi) | 12 |
| 2.4 Trametinib (MEKi)..... | 16 |
| 2.5 Rationale | 21 |
| 2.6 Correlative Studies Background | 22 |
| 3. PATIENT SELECTION..... | 24 |
| 3.1 Eligibility Criteria..... | 24 |
| 3.2 Exclusion Criteria | 27 |
| 3.3 Inclusion of Women and Minorities | 28 |
| 4. REGISTRATION PROCEDURES | 28 |
| 4.1 General Guidelines | 28 |

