| 2-mL blood per time point for pharmacokinetics (Section 9.5) ⁿ | | Please see Section 9.5 for details of time points | | | | | |
| Paraffin tumor block (Section 9.4) | X | | | | | | |

| 10-mL blood for BRAF mutations in circulating plasma (Section 9.2) | | X | | | X ^r | X (Cycles 3 and 5 only) | X Only if PD |
|---|---|---|--|---------------------------|----------------|----------------------------|-----------------|
| Tumor Pharmacodynamics Tumor Biopsy (Section 9.1) | X | | | X ⁱ +/- 5 days | | | |
| Tumor Mutation Screening Tumor Biopsy (Section 9.3) | | | | | | | X Only if PD |

- a. If pre-study labs (CBC/diff, Chemistry) are drawn within 14 days of study entry, such labs do not have to be repeated on C1D1.
- b. All on-study visits can be performed within +/-3 days. For cycles 8 to 18, please follow same schedule as for even and odd cycles as Cycles 2, 4, 6 or Cycles 3, 5, 7 respectively. Please review all footnotes as some testing is not required as frequently after 1st 6 cycles.
- c. Off-therapy evaluations are to be conducted within 4 weeks after last dose of study drug (s). Labs do not need to be repeated if done within 2 weeks.
- d. Sodium, Potassium, Chloride, Bicarbonate, Creatinine, BUN, Glucose, Calcium, Phosphorus, Total protein, Albumin, Total bilirubin, SGOT (AST), SGPT (ALT), Alkaline phosphatase, lactate dehydrogenase (LDH).
- e. Pregnancy test (sensitivity of at least 50 mIU/mL) will be performed for all women of childbearing potential before beginning study drug (s).
- f. CT or MRI scans as determined by investigators to assess the response per RECIST v1.1 criteria. CTs or MRIs with IV contrast are encouraged but will be done per investigator's discretion. Scans can be done within 7 days prior to day 1 of cycles 3, 5, 7 and subsequent odd number of cycles. If CT abdomen is negative at baseline, they only need to be repeated if clinically indicated during the study period.
- g. PET scans are performed only as clinically indicated at pre-study, every 8 weeks and off study as determined by treating physicians.
- h. Echo or MUGA will be done pre-study and every 2 cycles for 6 cycles and then every 4 cycles x 18 months and then only if clinically indicated. Scans can be done within 7 days prior to day 1 of cycles 3, 5, 7 and subsequent odd number of cycles.
- i. This can be done any time +/- 5 days from C1D15. Not required during C2D15 time point.

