In general, patients are followed every 2 weeks for the first 8 weeks and then every 4 weeks until the completion of cycle 18 at which time visits will be extended to every 8 weeks while on study. Off therapy visit is done within 4 weeks after last dose of study drug. Additionally, patients will be seen in the clinic, or contacted by phone every 3 months for 1 year post study treatment.

Follow up data to be collected:

- Survival status
- Disease status (progressed/stable)
- If any additional cancer therapy was initiated (name & start date)

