13.5 Reporting and Exclusions

- 13.5.1 Evaluation of toxicity – All patients will be evaluable for toxicity from the time of their first treatment with Dabrafenib on ARM A and from the time of their first treatment with Dabrafenib and Trametinib on ARM B.
- 13.5.2 Evaluation of response – All patients included in the study must be assessed for response to treatment, even if there are major protocol treatment deviations or if they are ineligible. Each patient will be assigned one of the following categories: 1) complete response, 2) partial response, 3) minor response, 4) stable disease, 5) progressive disease, 6) early death from malignant disease, 7) early death from toxicity, 8) early death because of other cause, or 9) unknown (not assessable, insufficient data). [Note: By arbitrary convention, category 9 usually designates the “unknown” status of any type of data in a clinical database.]

All of the patients who met the eligibility criteria (with the possible exception of those who received no study medication) should be included in the main analysis of the response rate. Patients in response categories 5-9 above should be considered to have a treatment failure (disease progression). Thus, an incorrect treatment schedule or drug administration does not result in exclusion from the analysis of the response rate.

All conclusions should be based on all eligible patients. Subanalyses may then be performed on the basis of a subset of patients, excluding those for whom major protocol deviations have been identified (e.g., early death due to other reasons, early discontinuation of treatment, major protocol violations, etc.). However, these subanalyses may not serve as the basis for drawing conclusions concerning treatment efficacy, and the reasons for excluding patients from the analysis should be clearly reported. The 95% confidence intervals should also be provided.

References

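### The toxicity comparison that feeds the regimen choice has no common time window or exposure adjustment, so unequal time on drug would distort it in a direction not known in advance

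*Combined protocol and SAP*

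**What the plan says.** Section 13.4 (Toxicity and Tolerability) gives the main summary: "The maximum grade for each type of toxicity will be recorded for each patient, and frequency tables will be reviewed to determine toxicity patterns". It adds that "The incidence of severe (grade 3+) adverse events or toxicities will be described", and it counts patients with dose modifications or delays and patients who stop for adverse reactions. For these tolerability measures, "we will explore differences in these measures between the arms". All are counts or proportions of patients ever affected. None is tied to a fixed period or divided by time on treatment.

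Sections 11.1.1 and 13.5.1 fix only the start of observation: "All patients will be evaluable for toxicity from the time of their first treatment with Dabrafenib on ARM A", with the equivalent for Arm B. Neither gives an end. The Schema makes treatment open-ended: "Continuous treatment until disease progression, unacceptable adverse event, consent withdrawal, or development of illness prohibiting further treatment".

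Section 13.1.3 gives toxicity two roles. It is one of four listed considerations when observed response rates fall within 0.10 of each other; the others are PR+CR rate, progression-free survival and correlative markers. It is also the one reason given for departing from a clear response winner: "The only potential exception is if the clearly most promising regimen has substantially more toxicity than the other regimen(s". What counts as substantially more is not defined. The primary endpoint in 13.1.2, by contrast, is confined to the first 6 cycles.

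**The concern.** A patient's maximum grade can stay the same or rise as observation lengthens; it cannot fall. The same holds for ever having a grade 3+ event, a dose change or a toxicity-related stop. When treatment runs until progression or intolerance, time on drug is itself an outcome of treatment and can differ between arms. The protocol hypothesises greater efficacy for the combination (Section 2.5), so longer exposure on Arm B is plausible. Two regimens with the same monthly risk of severe toxicity would then show different ever-affected proportions.

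What is at stake is the regimen recommendation. An arm could be marked down because its patients stayed on drug longer. Conversely, an arm whose patients stop early could appear safer than it is.

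**Working it through.** **1. How often toxicity can enter the choice.** Inputs from 13.1.3: 26 per arm, margin d = 0.10, half credit for an ambiguous result. With 26 per arm, ambiguous means a difference of at most 2 responders (2/26 = 0.077; 3/26 = 0.115). Exact enumeration of two independent Binomial(26, p) counts gives P(correct) + 0.5 × P(ambiguous):

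| True rates | Correct | Ambiguous | Wrong | Power | Plan states |
|---|---|---|---|---|---|
| 15% vs 35% | 0.814 | 0.181 | 0.006 | 0.904 | 90% |
| 10% vs 30% | 0.834 | 0.163 | 0.003 | 0.916 | >90% |
| 40% vs 60% | 0.779 | 0.206 | 0.016 | 0.882 | >88% |

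The plan's figures reproduce. Toxicity is a listed consideration in about 18% of trials at the design rates. If both arms share a true rate of 35%, 25% or 15%, it is one in 53%, 58% or 67%. In the remaining trials the override is available, and the stated power makes no allowance for it.

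**2. Size of a false gap.** The documents give no time-on-drug figures and no hazard for this population, so these inputs are assumptions: the same constant hazard h of a first grade 3+ event in both arms, and exponential time on drug with median m, so that the stopping rate is e = ln 2 / m. For m = 8 months, e = 0.0866; for m = 12 months, e = 0.0578. Take h = 0.06 per month.

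- Unlimited follow-up, h/(h+e): 0.06/0.1466 = 40.9% vs 0.06/0.1178 = 51.0%. Gap 10.0 points, about 2.6 patients of 26.
- Primary analysis of Section 13.2, when the last patient reaches 6 cycles after about 24 months' accrual. Assuming even accrual, follow-up is uniform from 5.5 to 29.5 months. Averaging h/(h+e) × (1 − exp(−(h+e)t)) over that range gives 35.9% vs 42.1%. Gap 6.2 points, about 1.6 patients.
- Fixed window of 6 cycles (168 days = 5.52 months), same formula at t = 5.52: 22.70% vs 24.35%. Gap 1.65 points.
- Events possible only in the first 3 months, same formula at t = 3: 14.6% vs 15.2%. Gap 0.6 points, rising to 1.5 at h = 0.20.
- First events per patient-month at risk: h in both arms. Gap 0.

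**3. Range.** For h of 0.03 to 0.10 and medians of 8–10 vs 12–16 months, the gap is 4 to 17 points with unlimited follow-up and 0.4 to 3.7 points within 6 cycles. At the primary analysis, the lowest case (h = 0.03, 10 vs 12 months) falls from 4.0 to 1.8 points; h = 0.06 with 8 vs 16 months falls from 17.2 to 10.0.

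**4. Direction.** Swapping the medians reverses the sign, and equal medians give zero.

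**The case against.** The case on the other side is substantial, and much of it stands.

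- **Direction is not established.** A reader might infer that Arm B is bound to look worse. The documents do not support that. Treatment also ends for unacceptable toxicity or for more than 28 days off drug (Section 5.5). The background data do not settle which arm stays on longer: no permanent stops for adverse events are reported in the two dabrafenib monotherapy studies (2.3.5.2), against 4% to 10% in trametinib combination trials with various partners (2.4.5.2).
- **Size depends on the data cut and on when events occur.** The 10-point figure assumes unlimited follow-up and a constant hazard. An earlier cut lowers it, and early-onset toxicity nearly removes it. The documents do not give the onset pattern. The sampling standard error of the difference at 26 per arm is about 14 points, larger than the distortion in the main example.
- **Thinning visits do not add to the false excess.** It is tempting to count the schedule as a second source of inflation: "patients are followed every 2 weeks for the first 8 weeks and then every 4 weeks until the completion of cycle 18", then 8-weekly, and "Echo or MUGA will be done pre-study and every 2 cycles for 6 cycles and then every 4 cycles x 18 months". Sparser late monitoring would detect fewer events in the longer-treated arm and so shrink the excess. The 8-weekly visits start only after cycle 18, beyond the medians assumed here.
- **Toxicity does not decide alone.** It is one of four considerations in the ambiguous zone, and if longer treatment reflects disease control, progression-free survival credits that arm in the same deliberation. The override is a judgement, not a numerical trigger.
- **Late toxicity matters.** Making a 6-cycle window the sole decision measure would discard it although treatment continues.

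None of this supplies a window or an exposure denominator, and a distortion in either direction is unwelcome.

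**Conclusion.** The concern holds in a conditional form. Section 13.4 compares the arms on cumulative ever-affected measures without a common window or exposure adjustment, and 13.1.3 uses toxicity in the regimen choice. If time on drug differs, the comparison is distorted against the longer-treated arm at equal hazards. The main example gives about 10 points with unlimited follow-up, about 6 at the primary analysis, and about 1 or less with early-onset events. These figures rest on assumed durations and an assumed common hazard; they do not predict what this trial will show. That the tables cover all time on drug is itself inferred from a stated start with no stated end. The documents do not support saying that the plan necessarily penalises the more effective arm. This is an inexpensive improvement to make before the data are seen, not a flaw that invalidates the design.

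**What to change.** In 13.4, keep the maximum-grade tables and add for each arm:

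1. grade 3+ events per patient-month on randomized treatment, or the cumulative incidence of a first grade 3+ event with stopping treatment as a competing event;
2. maximum grade within the first 6 cycles.

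Both should end at cross-over. Section 13.1.2 keeps post-cross-over data out of the decision analyses, but it does so while defining the response endpoint, and 13.4 does not say how it applies to toxicity.

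The two options under item 1 are not equivalent. The rate removes the duration effect if the hazard is roughly constant. The cumulative-incidence curve needs no such assumption, but under the model above its long-run value is the same h/(h+e), so it must be read at the same times in both arms.

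In 13.1.3, state that the toxicity comparison used for the regimen choice will be read from these tables together with the cumulative table and time on treatment. Late toxicity then still counts.

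The cost is SAP wording and a small amount of extra analysis of data already collected. The 6-cycle table reduces the distortion without fully removing it, and event rates are hard to interpret if the hazard changes markedly over time, which is why the tables should be read together.

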1.2. Secondary Objectives

- a. To understand duration of objective response, progression-free survival and overall survival for each treatment group.
- b. To assess tolerability and adverse events of Dabrafenib (BRAFi) as a single agent and the tolerability and adverse events of Dabrafenib (BRAFi) and Trametinib (MEKi) in combination, in patients with DTC.
- b. To evaluate impact of experimental drugs on serum tumor marker thyroglobulin and its correlation with overall response rate.
- d. To understand pharmacokinetic, pharmacogenetics and pharmacodynamics of experimental drugs using serial tumor biopsies, tumor blocks and peripheral blood.

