9.6.2 Shipping of Specimen(s): Frozen blood samples will be shipped on dry

ice to the Solid Tumor Translational Science (STTS) Resource at The Ohio State University Comprehensive Cancer Center along with tumor biopsies (if applicable) and with frozen plasma for BRAF mutation analysis. Shipping address and days of shipment details will be provided in the Lab Manual.

9.63 Site(s) Performing Correlative Study: Pharmacanalytical Shared Resource at the Ohio State University Comprehensive Cancer Center

9.64 Methods for Analysis of Pharmacogenetics: DNA will be extracted from frozen blood. Analysis for polymorphisms in drug metabolizing enzymes and transporter genes will be done using appropriate drug disposition (absorption, distribution, metabolism, elimination) genotyping panel(s). Dabrafenib is a substrate and inducer of CYP3A4 and information on the clearance pathways for Trametinib is limited.

10. STUDY CALENDAR:

| | Pre-therapy ^a (Days -28 to Day 0) | On-therapy ^b | | | | | Off-therapy ^c |
|---|---|---|-------------------------|-----------------------|---|---------------------------------------|--------------------------|
| | | Day 1 Cycle 1 ^l | Day 7 Cycles 1,2,3,4 | Day 15 Cycles 1, 2 | Day 1 Cycles 2, 4, 6 ^l Only first 18 Cycles ^p | Day 1 Cycles 3, 5, 7 ^{lp} | |
| Study Drug (s) | | See Section 5.0 for details | | | | | |
| History/Physical Exam | X | X | | X | X | X | X |
| Vital signs/Weight | X | X | | X | X | X | X |
| Concurrent Medications | X | X | | X | X | X | X |
| Adverse Event Evaluation | | X | | X | X | X | X |
| Patient diary Submission | | | | | X | X | X |
| CBC w/diff, platelets ^m | X | X ^a | | X | X | X | X |
| Serum Chemistry ^d | X | X ^a | | X | X | X | X |
| Serum β-HCG ^e | X | | | | | | |
| Serum Thyroglobulin (Tg), anti-Tg antibody and TSH | X | | | | | X | X |
| Dermatology Exam | X ⁱ | | | | | X ^j | |
| Ophthalmologic Exam | X ^k | | | | | | |
| Electrocardiogram (EKG) ^q | X | | | | | X | |
| CT or MRI scan of neck/chest/abdomen ^f | X ^f | | | | | X ^f | |
| PET scan (only if clinically indicated) ^g | X ^g | | | | | X ^g | |
| Transthoracic Echocardiogram or MUGA ^h | X ^h | | | | | X ^h | |
| Phone Call Visit ^o | | | X | | | | |
| | Following Correlative tests may be done in selected group of patients ONLY. (See Section 9 and Lab Manual) | | | | | | |
| 6-mL blood for Pharmacogenetics (Section 9.6) ⁿ | | X | | | | | |

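### The between-arm thyroglobulin comparison in Section 13.4 does not use the baseline value as a covariate and fixes neither scale nor visit; a baseline-adjusted log-scale analysis would be a small gain in precision at no cost

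*Combined protocol and SAP*

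**What the plan says.** Section 1.2 makes thyroglobulin a secondary objective: "To evaluate impact of experimental drugs on serum tumor marker thyroglobulin and its correlation with overall response rate". The Study Calendar (Section 10) has a row for "Serum Thyroglobulin (Tg), anti-Tg antibody and TSH", marked before therapy, on Day 1 of the odd cycles from cycle 3, and off therapy. A baseline value is therefore planned for every patient.

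Section 13.4 covers the analysis in three steps. It states that "change in serum thyroglobulin levels will be evaluated between arms". It then relates that change to response by logistic regression, with arm and thyroglobulin in the model. Finally it says that differences in levels will be examined with boxplots and "two-sample t-tests (or nonparametric equivalent as necessary").

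No covariate, transformation, visit or effect estimate is named for the comparison of arms. No significance level, power or decision rule is attached to it. Section 13.3 lists no stratification factors, so baseline thyroglobulin is not balanced by design.

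**The concern.** A comparison of arms on a continuous marker with a measured baseline is usually most precise when baseline enters as a covariate. With 26 patients per arm and no stratification, the arms can differ at baseline by chance. A change score over-corrects for such a difference whenever the regression slope of follow-up on baseline is below 1. A comparison of follow-up levels does not correct for it at all.

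Scale matters too. If the marker is strongly right-skewed, raw change is driven by the few patients with the highest baseline values. The section leaves open levels or change, raw or log scale, which visit, and t-test or rank test. All four could be settled after the data are seen, and a null result would then be hard to interpret.

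**Working it through.** **Inputs from the documents.** Allocation is 1:1 (Section 13.1.1), and "26 evaluable patients will be accrued to each arm" (Section 13.1.3). Thyroglobulin is drawn before therapy and first on treatment at Cycle 3 Day 1 (Section 10). The documents give no SD, correlation, effect size or power for thyroglobulin; all such values below are assumptions.

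**The plan's own figure.** The only stated power is for the primary endpoint: 90% at 15% versus 35%, with an observed lead of at least 0.10 deciding and ambiguous results credited one half. A lead of 0.10 with 26 per arm means at least 3 responders (3/26 = 0.115). Exact binomial enumeration gives 0.8138 + 0.5 × 0.1805 = 0.904, which reproduces the 90%. It says nothing about thyroglobulin.

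**Formulas.** Let the SD be equal at baseline and follow-up, with correlation rho. Per unit of SD², up to a common factor of 2/n, the variance of the arm difference is:

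- change score: 2(1−rho)
- follow-up level only: 1
- ANCOVA: 1−rho², times 1 + 1/(2n−4) for estimating the slope, which is 1 + 1/48 = 1.021 at n = 26

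Before that small penalty, ANCOVA/change = (1−rho²)/[2(1−rho)] = (1+rho)/2, and ANCOVA/level = 1−rho². The third column below includes the penalty; for example, at rho = 0.5 it is 1/√(0.75 × 1.021) = 1.143.

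| rho | ANCOVA/change variance | Excess standard error (SE) of change score | ANCOVA/level variance |
|---|---|---|---|
| 0.5 | 0.75 | 14% | 0.75 |
| 0.7 | 0.85 | 7% | 0.51 |
| 0.85 | 0.93 | 3% | 0.28 |
| 0.9 | 0.95 | 1.5% | 0.19 |

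The variance ratios against change correspond to 33%, 18% and 8% more patients at rho 0.5, 0.7 and 0.85 (1/0.75, 1/0.85, 1/0.925). Where ANCOVA has 80% power, the change t-test has 69%, 74% and 79% at rho 0.5, 0.7 and 0.9. A t-test on levels alone has 69%, 53% and 23%. With 20 per arm the results are nearly the same.

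**If the SDs differ.** With k = follow-up SD / baseline SD, ANCOVA/change = (1−rho²)k²/(1+k²−2·rho·k). For rho 0.5 to 0.9 this is 0.50–0.56 at k = 0.75 and 0.14–0.25 at k = 0.5. On the raw scale, k well below 1 would follow if treatment lowers thyroglobulin in proportion to its baseline.

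**Scale, by simulation.** Assumed: lognormal values, natural-log SD 1.5, common shift −0.7, a further 2-fold fall in Arm B, 26 per arm, 4,000 trials per cell, two-sided 5% tests.

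| Analysis | rho 0.5 | rho 0.7 | rho 0.85 |
|---|---|---|---|
| t-test, raw change | 7% | 8% | 8% |
| rank test, raw change | 16% | 19% | 24% |
| rank test, percent change | 34% | 54% | 82% |
| t-test, log change | 38% | 57% | 84% |
| ANCOVA, log scale | 47% | 63% | 87% |

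On the log scale, baseline adjustment adds 9, 6 and 3 percentage points. The rest of the distance from the first row is due to the scale.

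**The case against.** Three arguments on the other side have force.

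First, a reader might infer that the plan specifies a t-test on raw change. The documents do not say this. The sentence on change names no test. The t-test is attached to differences in levels, directly after the text on response, and could even mean responders against non-responders. Change could equally be percent or log change, and a rank test on percent change performs close to the log-change t-test. This stands: the 7–24% powers describe one possible reading and are not a property of the plan. It does not remove the gap, because none of these readings uses baseline as a covariate when the arms are compared.

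Second, a reader might infer that omitting the covariate costs much precision. A change score already uses baseline, and with equal SDs and rho of 0.7 or more its SE is at most about 7% larger. This also stands.

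Third, under randomisation the unadjusted comparison is unbiased. Chance imbalance costs precision, which the variance ratios already count, and is not a separate defect. The objective in Section 1.2 states no between-arm hypothesis, and Section 13.4 treats thyroglobulin as a correlative marker. Nor is thyroglobulin named among the factors that Section 13.1.3 lists for an ambiguous primary result. All of this limits the importance of the point. It is not a reason to leave a collected baseline out of the comparison.

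**Conclusion.** The point holds as a minor one. Section 13.4 plans a between-arm evaluation of change in thyroglobulin, names only unadjusted tests, and leaves scale and visit open, although a baseline value is scheduled for every patient. On the log scale with equal SDs, ANCOVA has 0.75 to 0.93 of the variance of a change score for rho 0.5 to 0.85, and 0.75 to 0.28 of the variance of a comparison of levels alone.

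These figures rest on assumed rho and equal SDs. Against a change score the gain is negligible when rho is close to 1, and large when the follow-up SD is well below the baseline SD or when untransformed skewed values are tested. The documents do not show which case applies, so no single figure for lost power should be quoted. The primary decision rule, its 90% power and the 52-patient sample size are unaffected.

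**What to change.** In Section 13.4, replace the wording on the thyroglobulin comparison with the following:

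- Analyse log thyroglobulin at Cycle 3 Day 1, the first scheduled on-treatment draw, by ANCOVA with arm and baseline log thyroglobulin.
- Report the between-arm geometric-mean ratio with its 95% CI.
- Show Cycle 5 Day 1 and Cycle 7 Day 1 descriptively. By then some patients will have stopped treatment, and some Arm A patients may have crossed over.
- Use the log ratio to baseline as the thyroglobulin term in the planned logistic model with arm.
- State which groups the t-test or rank test compares, if it is kept.

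The cost is an edit to the analysis text before the data are examined. It needs no new samples, visits or patients.
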